I assure the HIC that the principal investigator and all members of the research team are qualified by education, training, licensure and/or experience to assume participation in the conduct of this research trial. I also assure that the principal investigator has departmental support and sufficient resources to conduct this trial appropriately.
Chair Name (PRINT) and Signature Date
Chair Name (FRIVI) and Signature
Department
YNHH Human Subjects Protection Administrator Assurance Statement
Required when the study is conducted solely at YNHH by YNHH health care providers.
As Human Subject Protection Administrator (HSPA) for YNHH, I certify that:
I have read a copy of the protocol and approve it being conducted at YNHH.
 I agree to notify the IRB if I am aware of any real or apparent institutional conflict of interest. The principal investigator of this study is qualified to serve as P.I. and has the support of the hospital
for this research project.
YNHH HSPA Name (PRINT) and Signature Date

SECTION V: RESEARCH PLAN

1. **Statement of Purpose:** State the scientific aim(s) of the study, or the hypotheses to be tested.

This is a four week, randomized, placebo controlled, crossover trial comparing cannabidiol (CBD) to placebo in outpatients with psychotic disorder within their first five years of disease onset. We hypothesize that treatment with CBD will result in:

- a. Primary Hypotheses:
 - i. Improvement evidenced by a reduction in scores on the Positive and Negative Syndrome Scale for Schizophrenia (PANSS).
 - ii. Improvement evidenced by a reduction in the Clinical Global Impression of Severity scale (CGI).
- b. Secondary Hypothesis:
 - i. Greater improvement in functioning as measured on the "Patient Assessment of Own Functioning Inventory: (PAOFI) and the Quality of Life Scale (QLS)
 - ii. No worsening of depressive symptoms or suicidality as measured on the CDSS and CSSRS.
- c. Exploratory Hypotheses:
 - i. Exploration of the effect of CBD on EEG recordings of MMN and P300 amplitude and latency, known endophenotypes/biomarkers of Schizophrenia
- 2. **Background:** Describe the background information that led to the plan for this project. Provide references to support the expectation of obtaining useful scientific data.

There is a need to develop anti-psychotic therapeutics with novel mechanisms of action and fewer side effects:

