DSMB: A Data Safety Monitoring Board is being assembled for this study. Unblinded safety data will be provided to the committee for monitoring purposes, in a meeting that will be held approximately every 6 months. DSMB reports will be provided to the HIC.

11. Statistical Considerations:

General Strategy:

All outcomes will be summarized descriptively and assessed for normality prior to analysis using normal probability plots and Kolmogorov test statistics. Transformations or nonparametric analyses will be performed as necessary. All tests will be two-sided and considered statistically significant at alpha=.05. Post-hoc comparisons will be performed as appropriate and significance levels for secondary analyses will be adjusted for multiple tests using the Bonferroni correction. All analyses will be performed using SAS, version 9.3 (SAS Institute Inc., Cary, NC).

Linear mixed models will be used assess symptom improvement as measured by the PANSS (primary hypothesis) and CGI. In these models group (CBD vs. placebo) and time (see study time points) will be modeled as within-subjects factor. Oder effects will also be tested. Least squares means and standard errors will be calculated in the mixed model and plotted to interpret significant effect. A significant group by time interaction explained by reduced symptoms over time due to CBD treatment will be supportive of our hypothesis. In the above models, the best fitting variance-covariance structure will be selected based on information criteria. The mixed effects approach is advantageous in that it is unaffected by randomly missing data and allows greater flexibility in modeling the correlation structure of repeated measures data [31]. Similar mixed models as described above will be employed to evaluate secondary outcomes (e.g., PAOFI, EEG parameters).

Power Analysis:

We will recruit 36 subjects and randomly assign 18 to receive either CBD followed by placebo (order 1) or placebo followed by CBD (order 2). Based on a within-subjects design and a two-tailed alpha=0.05, 36 subjects will provide 80% power to detect moderate treatment effects as small as d'=0.49. This compares favorably with the effects (d=0.7) observed by Leweke in their study comparing CBD to amisulpiride in schizophrenia patients.

SECTION VI: RESEARCH INVOLVING DRUGS, BIOLOGICS, RADIOTRACERS, PLACEBOS AND DEVICES

If this section (or one of its parts, A or B) is not applicable, state N/A and delete the rest of the section.

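### PANSS and CGI-S are both listed as primary hypotheses, but the statistical section labels only PANSS primary and gives no success rule for the pair

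*Combined protocol and SAP*

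**What the plan says.** Section V item 1 (Statement of Purpose) has a plural heading for the primary hypotheses and lists two of equal rank. The first is "Improvement evidenced by a reduction in scores on the Positive and Negative Syndrome Scale for Schizophrenia (PANSS"). The second is "Improvement evidenced by a reduction in the Clinical Global Impression of Severity scale (CGI").

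Section V item 11 (Statistical Considerations, General Strategy) introduces the mixed models for "PANSS (primary hypothesis) and CGI", so the label is singular and attached to PANSS only. I take CGI there to mean the severity scale named in item 1. The same section states: "All tests will be two-sided and considered statistically significant at alpha=.05". Its multiplicity rule is that "significance levels for secondary analyses will be adjusted for multiple tests using the Bonferroni correction". Success is defined in one sentence: "A significant group by time interaction explained by reduced symptoms over time due to CBD treatment will be supportive of our hypothesis". Other outcomes follow with: "Similar mixed models as described above will be employed to evaluate secondary outcomes (e.g., PAOFI, EEG parameters"). CGI is not among those examples.

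The Power Analysis covers one test at an unsplit alpha: "Based on a within-subjects design and a two-tailed alpha=0.05, 36 subjects will provide 80% power".

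Neither item states an either-or-both rule, a testing order or a division of alpha between the two measures.

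**The concern.** The two sections disagree on whether CGI-S is primary, and that status decides whether the Bonferroni sentence reaches it. Read with item 1, CGI-S is primary, escapes the correction and is tested at a full 0.05 beside PANSS. Read with item 11, it is probably secondary and is adjusted.

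The case that matters is CGI-S positive with PANSS negative. Item 1 would support calling that a primary success; item 11 leans against it. With no rule fixed in advance, the reading could be chosen once the results are known, and 0.05 would no longer be the error rate of the primary claim.

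**Working it through.** **1. The plan's own figure.** Inputs from the Power Analysis: n = 36, within-subject comparison, two-sided alpha 0.05, d' = 0.49, power 80%. For a paired t-test with 35 degrees of freedom the noncentrality is 0.49 × √36 = 2.94, which gives power 81.6%. The effect detectable with 80% power is 0.480. The stated figure is reproduced to within 2 points, and it belongs to a single test at 0.05.

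**2. Error if either measure suffices.** Let Z1 (PANSS) and Z2 (CGI-S) be standard normal under no effect, with correlation r and critical value 1.96. The documents give no r, so I show a range.

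- Either significant, two-sided: 1 − P(both absolute values below 1.96). At r = 0 this is 1 − 0.95² = 0.0975.
- Either significant in favour of CBD: 1 − P(Z1 < 1.96 and Z2 < 1.96). At r = 0 this is 1 − 0.975² = 0.0494.
- False benefit claim on CGI-S alone, PANSS not significant for benefit: the previous figure minus 0.025.

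| r (assumed) | Either, two-sided | False CBD benefit | Of which CGI-S alone |
|---|---|---|---|
| 0 | 9.75% | 4.9% | 2.4% |
| 0.5 | 9.1% | 4.5% | 2.0% |
| 0.7 | 8.3% | 4.2% | 1.7% |
| 0.9 | 7.0% | 3.5% | 1.0% |
| 0.95 | 6.5% | 3.2% | 0.7% |
| One test only | 5.0% | 2.5% | – |

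Simulated paired t-tests with n = 36 (200,000 trials per r) give 9.7%, 9.1%, 8.3%, 7.1% and 6.4% for the two-sided column. Whatever the correlation or form of test, the two-sided error cannot exceed 0.05 + 0.05 = 10%.

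**3. Error under the other rules.**

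- PANSS sole primary, or first in a fixed sequence: 5% (4.9% to 5.1% in simulation).
- Both required, two-sided, neither effect real: 0.10 minus the either-suffices figure, so 0.25% at r = 0 and 3.5% at r = 0.95. If one effect is real and large, the error on the other approaches 5% but does not exceed it.
- Alpha of 0.025 each: at most 5%; 1 − 0.975² = 4.94% if independent.

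**4. The planned test has more than one degree of freedom.** The group-by-time interaction over five visits (II to VI) has 4. A simplified stand-in (Hotelling T² on four contrasts, n = 36, the same r for each contrast) gives 9.8%, 9.3%, 8.7%, 7.4% and 6.7% two-sided. The result hardly changes.

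**5. Power under each rule**, assuming both true effects are d' = 0.49, with one-degree-of-freedom tests.

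- PANSS alone at 0.05: 81.6%.
- CGI-S after a significant PANSS, which is the same event as both significant: 71%, 73%, 77% and 78% at r = 0.5, 0.7, 0.9 and 0.95. At r = 0 it is 0.8155² = 66.5%.
- Each at 0.025: 72.3% per measure. The detectable effect rises to 0.533, and about 43 subjects would be needed for 80% power at 0.49.

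**The case against.** The strongest reply is that item 11 already settles the matter. It uses the singular for the primary hypothesis and again in the success sentence, and it sets power at an undivided 0.05. On that reading CGI is secondary, Bonferroni covers it and the primary error is 5%. Its absence from the secondary examples proves little, because they are only examples. No sentence says that either measure alone is enough, so the inflated error belongs to a rule the plan never states. One could also treat the two hypotheses as separate questions, each with its own 5%.

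Much of this stands. Item 11 does favour PANSS alone, and the inflation is conditional. The tabulated range also rests on an assumed correlation. Both scales are clinical ratings of the same patients at the same visits, so r near 0 is the less likely end. Nor is 6.5% a floor: at r = 0.99 the figures are 5.7% two-sided and 2.8% for false benefit.

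What the reply does not remove is the contradiction. Item 1 is the plan's statement of hypotheses, and nothing in item 11 withdraws CGI-S from it. Item 11 also puts CGI in the same sentence and models as PANSS without calling it secondary. If two separate primary claims are intended, the plan should say so and accept the combined error.

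**Conclusion.** The concern holds. The conflict between items 1 and 11 and the missing success rule are plain on the page and need no assumption. The size is conditional: it applies if either measure may support the primary claim, and it depends on the assumed correlation. At r = 0.7 to 0.9 the two-sided error would be 8.3% to 7.0% and the chance of a false benefit claim 4.2% to 3.5% instead of 2.5%. The excess of 1.7 to 1.0 percentage points is a false benefit claim resting on CGI-S alone. If PANSS is the sole primary, or both are required, there is no inflation. The error figures are for one-degree-of-freedom tests, supported by the 4-degree-of-freedom stand-in. The power of the planned interaction test cannot be computed from the documents. This should be fixed before unblinding, and it is cheap to fix.

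**What to change.** Make items 1 and 11 agree, following the label that item 11 already uses:

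- PANSS is the sole primary outcome, tested at two-sided 0.05 with the planned mixed model.
- CGI-S is tested at two-sided 0.05 only if PANSS is significant.
- Bonferroni applies to the remaining secondary analyses.

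This takes one or two sentences. It leaves the model, sample size, PANSS alpha and stated power basis as they are, and holds the error for the pair at 5%. It is nevertheless a decision for the sponsor and not just a change of wording. CGI-S loses its place as a primary hypothesis, is tested outside the Bonferroni rule, and cannot be claimed as confirmatory if PANSS fails. Under the assumptions in step 5, the chance of a confirmatory CGI-S claim becomes 71% to 78% for r = 0.5 to 0.95, against about 82% if it were tested alone.

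If the sponsor prefers to keep both as primary, two other rules close the gap at a higher cost to the primary claim. Requiring both gives about 66.5% (r = 0) to 78% (r = 0.95) power. Splitting alpha at 0.025 each gives 72% per measure. Either would require the power statement to be revised.

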- **4.** Columbia Suicide Severity Rating Scale (CSSRS) (Visits I-VI): The CSSRS is an interview based rating scale to systematically assess suicidal ideation and suicidal behavior. Versions are available for Screening/Baseline and follow-up visits.
- 5. Quality of Life Scale (QLS) (Visits II-VI): The QLS is a structured interview providing clinician ratings of function in key areas of everyday living.
- 6. The Patient Assessment of Own Functioning Inventory: (PAOFI) (Visits II-VI): will be included as a subjective assessment of cognitive functioning. The PAOFI is a widely used self-report instrument that taps into the respondent's own views and experiences regarding difficulty in everyday functioning.
- 7. Motor side effect scales (Visits I-VI): Barnes Akathisia Scale, Simpson Angus Scale, and the AIMS; Further, the UKU side effects scale will be administered at weekly visits to assess for antipsychotic induced side effects.
- 8. Metabolic parameters (Visits I, II, IV, VI): Appetite and food intake ratings (VAS) and three day dietary record (which have been shown to be predictors of energy intake and weight loss [30]), weight, fasting glucose and lipid profile.
- 9. Smoking and Cannabis use (Visits I-VI): Past week Time Line Follow Back approach.
- **10. EEG testing:** The main EEG outcome measures will be P50, P300 and ASSR as discussed above. Brain wave activity during tasks involved in the processing auditory and visual stimuli with different degrees of attentional and memory demands will be recorded. Auditory stimuli will include tones, white noise bursts, other digitized sounds (such as dog barks, rooster crows), or spoken words. Visual stimuli will include letters, numbers, words, geometric shapes, colored patterns, or photographic images. Some audiovisual stimuli may have emotive/emotionally salient or neutral content. Stimuli will be separated by intervals of .5 to 30 seconds. Some stimuli will require a button-press response using a response pad. These may be target stimuli in target detection tasks, or recalled stimuli in memory tasks. The EEG session will last approximately 2 hours.

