	Distributes the investigational device to subjects enrolled in the IRB-approved protocol:					
		SECTION VII: RECRUI	ITMENT/CONSENT AND ASSENT PROCEDURES			
Ta	Targeted Enrollment: Give the number of subjects: a. targeted for enrollment at Yale for this protocol Approximately 70 to have 36 completers b. If this is a multi-site study, give the total number of subjects targeted across all sites N/A					
Inc	Indicate recruitment methods below. Attach copies of any recruitment materials that will be used.					
	YCCI Recruitm Other (describe)	enter Newsletters ent database :	 ✓ Internet/Web Postings Mass E-mail Solicitation Departmental/Center Website Departmental/Center Research Boards ✓ Web-Based Clinical Trial Registries ✓ Clinicaltrials.gov Registry (do not send management) 	Radio Telephone Television Wewspaper aterials to HIC)		
Re	ecruitment Procedures:					

3.

1.

2.

a. Describe how potential subjects will be identified.

Potential subjects will be identified through responses to the methods of advertisements listed above. An additional document with the language used for internet/web postings has been included. Furthermore, the research team will reach out to local mental health facilities (including the Connecticut Mental Health Center, the West Haven VA and the Institute of Living) through "lunch and learns", etc. for patient referrals. A lunch and learn is a meeting that research staff schedule with clinicians and therapists at local mental health facilities where an overview of current research protocols are presented and discussed.

b. Describe how potential subjects are contacted.

Subjects will be asked to contact research staff through the advertisement methods listed above. In the event that a subject responds to an advertisement, they will be contacting study staff. In the event that subjects are referred from clinics or mental health facilities, research staff will require that the subjects' clinician contacts the subject first and then refers the subject to the research clinic.

c. Who is recruiting potential subjects?

Members of the research team.

4. Screening Procedures

- a. Will email or telephone correspondence be used to screen potential subjects for eligibility prior to the potential subject coming to the research office? ⊠Yes ☐No

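### The Bonferroni rule for secondary analyses makes no exception for harms, so it makes a reassuring null on depression and suicidality easier to reach

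*Combined protocol and SAP*

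**What the plan says.** **General rule.** Section V, 11 (General Strategy) sets one threshold: "All tests will be two-sided and considered statistically significant at alpha=.05". It then adds that "significance levels for secondary analyses will be adjusted for multiple tests using the Bonferroni correction". It neither defines the family of tests nor sets safety comparisons apart.

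**Tiers.** Section V, 1 makes PANSS and CGI severity the primary hypotheses. The secondary hypotheses cover two benefits (PAOFI and QLS) and one harm question, that CDSS and CSSRS show no deterioration. EEG is exploratory there.

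**Side-effect and metabolic measures.** These stand in the numbered list of outcome measures in Section V. Item 7 reads "Motor side effect scales (Visits I-VI): Barnes Akathisia Scale, Simpson Angus Scale, and the AIMS", and the UKU scale is added at weekly visits. Item 8 reads "Metabolic parameters (Visits I, II, IV, VI): Appetite and food intake ratings (VAS) and three day dietary record", followed by weight, fasting glucose and lipids. Neither item is labelled primary, secondary, exploratory or safety. The statistical section names none of these measures. Its only examples of secondary outcomes are in this sentence: "Similar mixed models as described above will be employed to evaluate secondary outcomes (e.g., PAOFI, EEG parameters".

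**The concern.** Bonferroni guards against false positive claims. For an efficacy endpoint that is the error to guard against. For a harm question the costly error is the opposite one, missing a real worsening, and a smaller alpha makes that error more likely.

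The problem is clearest for CDSS and CSSRS. Their hypothesis is supported by finding no worsening, yet the plan offers only significance tests and sets no margin or interval criterion. Each extra test in the family makes it harder to reject the null, and so easier to report the result the hypothesis hopes for. The primary benefits carry no stated adjustment.

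Tolerability is a large part of the case for CBD in the Background. The placebo justification in Section VI expects some participants to take no other medication. A non-significant adjusted result on a harm scale could be taken as support for good tolerability when it mainly reflects a strict threshold and 36 subjects.

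**Working it through.** **Inputs from the Power Analysis (Section V, 11).** "We will recruit 36 subjects and randomly assign 18 to receive either CBD followed by placebo (order 1) or placebo followed by CBD (order 2"; each subject receives both treatments. The test is two-tailed at 0.05, and "36 subjects will provide 80% power to detect moderate treatment effects as small as d'=0.49". Section VII describes the target as "Approximately 70 to have 36 completers", so 36 is taken as the analysed number.

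**Assumptions.** The number of tests k is not in the plan. A paired t-test stands in for the mixed model. The plan gives no effect size for a harm, so its own d'=0.49 is used.

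**Step 1: reproduce the stated power.** For a paired t-test, the noncentrality is d × √n = 0.49 × 6 = 2.94, with df = 35. The two-sided 0.05 critical value is 2.030. The noncentral t gives power of 81.6%, against the stated 80%. The smallest effect detectable with 80% power is d=0.48. The plan's figure is sound.

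**Step 2: apply Bonferroni.** Use the same formula with alpha = 0.05/k. The smallest observed difference that would be flagged, in SDs of the within-subject difference, is the critical t divided by √36.

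| k | Family assumed | Alpha | Critical t | Smallest observed d flagged | Power at d=0.49 | d detectable at 80% power |
|---|---|---|---|---|---|---|
| 1 | no adjustment | 0.05 | 2.030 | 0.34 | 81.6% | 0.48 |
| 4 | PAOFI, QLS, CDSS, CSSRS | 0.0125 | 2.633 | 0.44 | 62.2% | 0.58 |
| 9 | for example, four side-effect scales and five metabolic measures | 0.0056 | 2.955 | 0.49 | 50.2% | 0.64 |
| 13 | those nine plus the four named instruments | 0.0038 | 3.096 | 0.52 | 45.0% | 0.66 |

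**Step 3: read the k=4 row as a risk of missing harm.** This row needs no inference about the unlabelled scales, only one test for each named secondary instrument. The chance of a non-significant result when CDSS or CSSRS truly worsens by d=0.49 is 100 − 81.6 = 18.4% unadjusted and 100 − 62.2 = 37.8% adjusted. It roughly doubles.

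**Step 4: cost of not adjusting harms.** With k independent tests and no true effect, the chance of at least one false signal is 1 − 0.95^k. That is 18.5% for k=4 and 37.0% for k=9. If CDSS and CSSRS join the nine side-effect and metabolic measures, k=11 and it is 43.1%.

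**The case against.** Several points on the other side stand.

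- **The unlabelled scales.** Nothing in the documents calls the motor, UKU or metabolic measures secondary. The Bonferroni clause shares a sentence with post-hoc comparisons and could be read as covering only follow-up tests. Against this, the statistical section uses the word secondary for EEG, which Section V, 1 calls exploratory, so its use reaches beyond the declared secondary hypotheses. That these scales fall under the rule is a reasonable inference, not a stated fact.
- **Harms against benefits.** A reader might infer that harms face a stricter threshold than benefits in general. The documents do not support that: PAOFI and QLS are benefits under the same adjustment. The contrast holds only against PANSS and CGI.
- **Other routes for safety data.** A reader might also infer that safety data have no other place in the plan. All outcomes are to be summarised descriptively. Section V has a separate Safety Assessment. The Data and Safety Monitoring Plan provides for graded adverse events, at least quarterly investigator review, and a DSMB that sees unblinded safety data about every six months. None of these uses a significance threshold. They do not replace an end-of-trial comparison of CBD with placebo, and the plan does not say whether rating-scale or metabolic data reach the DSMB.
- **More scales, less harm reported.** This does not follow in general. Per-test power falls with k, but the chance of at least one flag depends on how many scales are affected and how they correlate. If four independent scales all worsened by d=0.49, that chance would be 1 − 0.378^4 = 98%, against 81.6% for a single unadjusted scale.

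The CDSS and CSSRS point survives all of these unless the clause is confined to post-hoc tests, and the text does not say that it is.

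**Conclusion.** The concern holds in a limited form. The plan adjusts secondary analyses without exempting harms, and it expressly places one harm question, CDSS and CSSRS, in the secondary tier with no criterion for concluding that there is no worsening. Following the stated rule makes the reassuring result easier to obtain. For the motor, UKU and metabolic measures, the firm finding is that no tier and no treatment comparison are specified; that Bonferroni applies to them is only possible.

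For a harm of d=0.49, per-test power falls from about 82% to 62% with four tests and to 50% with nine. These figures rest on an assumed k, on 36 analysed subjects, on the paired t-test as a stand-in for the mixed model, and on borrowing the plan's detectable effect as the size of a harm. The direction does not depend on them. This is a cheap improvement to the plan and does not undermine the trial's design or its primary analysis.

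**What to change.** Amend the General Strategy in three ways:

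1. Limit the Bonferroni correction to the secondary efficacy hypotheses (PAOFI and QLS), and state the number of tests in that family.
2. For CDSS, CSSRS, the motor scales, UKU, the metabolic measures and adverse events, report the within-subject difference between CBD and placebo, or paired proportions for binary data, with unadjusted 95% confidence intervals.
3. State that a non-significant harm comparison will not be read as absence of harm.

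This takes a few sentences and changes nothing in the visits, measurements or sample size. The price is more nominal false alarms on harms, at the rates in Step 4 if the tests are independent. Reporting estimates with intervals instead of significance verdicts softens that price.

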Medical and Psychiatric Evaluation: Once written informed consent has been obtained, the diagnosis will be confirmed by a Structured Clinical Interview for DSM IV (SCID). A detailed medical and psychiatric history, physical examination (including vital signs, height, and weight), an electrocardiogram, and laboratory assessments (standard screening blood tests: CBC with differential and platelet count, electrolytes, creatinine, BUN, liver enzymes, T4, calcium, phosphate, TSH, and magnesium levels) will be performed. In addition, a full lipid profile, fasting glucose and insulin levels will be obtained. A pregnancy test will be done in all premenopausal women. A routine urinalysis and drug screen will be done as part of the screening process.

Subjects will be administered the PANSS and motor side effects scales (AIMS, Barnes akathisia scale, Simpson Angus scale). IQ will be measured at screening using the Wechsler Test of Adult Reading (WTAR). Subjects will also be asked to provide an informant who can be contacted to collect clinical and safety information relevant to the outcome measures on each visit. This could be a clinician or a family member/friend who sees the patient at least on a weekly basis.

Study Design: In this 2 period cross over design, subjects will be randomized in a 1:1 ratio to receive either: **Order 1**: CBD (Period 1) followed by placebo (Period 2) or **Order 2**: Placebo (Period 1) followed by CBD (Period 2) under double-blind conditions. The 2 study periods will be separated by a washout of at least 2 weeks. During each period subjects will receive study medications (CBD [total 800mg/day] or placebo) for a period of 4 weeks. This dose is within the dose range of doses that have been shown to be effective and safe. Randomization to the order of medication assignment will be stratified by baseline PANSS scores.

Study Visits:

Subjects will have the following visits during each period except for Visit I (screening), which will occur only at the beginning of their participation in the study:

Visit I: Screening (At least two visits: Visit Ia and Visit Ib.)

Visit II: Baseline: Will initiate treatment with study drug following baseline assessments.

(Visits III, IV, V: Weekly clinical evaluation and study medication refill)

Visit III: (Week 1)

Visit IV: (Week 2)

Visit V: (Week 3)

Visit VI: (Week 4): End of treatment period visit

Visit VII: Safety Follow up at week 5.

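### The crossover mixed model names no period or period-by-time term, and the order test that might supply one is undefined

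*Combined protocol and SAP*

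**What the plan says.** In Section V, item 11 (Statistical Considerations, General Strategy), the linear mixed models for PANSS and CGI are specified by two factors and one further sentence: "group (CBD vs. placebo) and time (see study time points) will be modeled as within-subjects factor. Oder effects will also be tested". The result that counts in favour of CBD is the interaction: "A significant group by time interaction explained by reduced symptoms over time due to CBD treatment will be supportive of our hypothesis". The error structure is left open: "the best fitting variance-covariance structure will be selected based on information criteria". Similar models are to be used for the secondary outcomes.

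Order has a meaning. The Power Analysis paragraph uses it for the two sequences, "CBD followed by placebo (order 1) or placebo followed by CBD (order 2"), and Study Design does the same. What is missing is the form of the order test, its level, and what follows from its result.

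Under Study Visits, "Subjects will have the following visits during each period except for Visit I (screening", which takes place once at the start). PANSS and CGI are collected at Visits I to VI, so Visits II to VI give five efficacy time points that recur under the same labels in each period. No period, period-by-time or sequence-by-time term is named anywhere in the documents.

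**The concern.** In a two-period crossover each subject's CBD-minus-placebo difference also contains a Period 1 versus Period 2 difference. It has one sign in one order and the opposite sign in the other. If the model has no term for it, two things can happen:

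- **Orders equal in size.** The period difference averages out of the treatment estimate but can inflate the error, so power falls and the test becomes conservative.
- **One order loses more data.** The period difference no longer averages out, and part of it is counted as drug effect.

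The declared contrast is a change over weeks, so a constant level shift between periods is harmless. What matters is a different course over the weeks in the two periods, for example a larger non-specific improvement in Period 1. The plan relies on mixed models being robust to data missing at random. That property needs a correctly specified mean model, and a real but omitted period-by-time difference breaks it.

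**Working it through.** **1. The plan's own power figure.** Inputs from the Power Analysis: n = 36, d' = 0.49, two-sided alpha 0.05, within-subjects. Noncentrality = 0.49 × √36 = 2.94. A paired t-test with 35 df has power 81.6%, which agrees with the stated 80%. Its critical value is about 2.03.

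**2. Does any reading of the order test adjust for period?** Code order s, group g and period p as ±1, with s = +1 for CBD first, g = +1 for CBD and p = +1 for Period 1.

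| Order | Period | s | g | p | s × g |
|---|---|---|---|---|---|
| CBD first | 1 | +1 | +1 | +1 | +1 |
| CBD first | 2 | +1 | −1 | −1 | −1 |
| Placebo first | 1 | −1 | −1 | +1 | +1 |
| Placebo first | 2 | −1 | +1 | −1 | −1 |

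Order-by-group therefore equals period. A rank check of the design with 2 orders, 2 periods and 5 visits gives the following.

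| Added to group, time, group-by-time | Contains period | Contains period-by-time |
|---|---|---|
| nothing | no | no |
| order | no | no |
| order, order-by-time | no | no |
| order, order-by-group | yes | no |
| order-by-time and order-by-group-by-time | yes | yes |

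Only the last form protects a group-by-time contrast.

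**3. Balanced, complete data (18 + 18).** The documents give no size for a period difference. Assume that week-4-minus-baseline change differs between periods by π, in SDs of the paired difference in change. The order means are then d' − π and d' + π. Their average is d', so there is no bias.

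*Unstructured-type error.* The variance estimate rises from 1 to about 1 + π² × 36/35. At π = 0.5 this is 1.257 (square root 1.121), and power is about Φ(2.94 − 2.03 × 1.121) = Φ(0.66) = 75%. Simulation (100,000 runs per scenario) gives:

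| π | Power without the term | Power with the term | Type I error without the term |
|---|---|---|---|
| 0 | 81.7% | 81.6% | 4.9% |
| 0.25 | 79.8% | 81.5% | 4.4% |
| 0.5 | 74.2% | 81.3% | 2.9% |
| 0.75 | 65.3% | 81.7% | 1.5% |
| 1.0 | 52.4% | 81.6% | 0.6% |

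*Subject, subject-by-period and residual variances only (assumed 0.6, 0.2, 0.2).* Power without the terms at π = 0.25, 0.5, 0.75 and 1.0 is 83, 82, 81 and 79%, against 83–84% with them. Type I error without them is 5.0, 4.5, 4.0 and 3.5%.

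A level shift of 1.0 leaves power at 82% with or without the terms.

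**4. Unequal loss.** Assume that 6 of 18 in the placebo-first order leave after Period 1. CBD then has 12 of its 30 records in Period 2, and placebo has 18 of 36. The bias in the week-4 contrast per unit difference in change (Period 2 minus Period 1) is 12/30 − 18/36 = 0.40 − 0.50 = −0.10. It is −0.15 if subject slopes persist across periods. If improvement is larger in Period 1, this favours CBD; more loss from the other order reverses the sign.

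- A plain period term leaves −0.10 (−0.15). Period-by-time gives 0.
- If the same 6 leave after week 1 or 2 of Period 2, the bias is −0.08 to −0.13 per unit difference in change and −0.02 to −0.04 per unit level shift.
- A pure level shift with loss after Period 1 leaves the week-4 contrast at about 0. It biases the average CBD–placebo difference by −0.16 to −0.18 per unit, but that is not the declared contrast.

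On paired differences from completers only, bias = π(n2 − n1)/(n1 + n2). At 22:14 and π = 0.5 this is 0.5 × (−8)/36 = −0.111. Power is 51.2% without the term against 79.5% with it, and type I error is 6.6% against 5.0%.

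**5. Cost of the terms.** With complete data, power goes from 81.6% (35 df) to 81.5% (34 df). With variance components, residual df go from 280 to 276 and power stays at 83%. With the loss in step 4, a change score has variance 2 × 0.2 = 0.4.

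- Without the terms: SE = √[0.4 × (1/30 + 1/36)] = 0.1563.
- With them: the within-period comparisons have variances 0.4 × (1/18 + 1/18) = 0.0444 and 0.4 × (1/12 + 1/18) = 0.0556. Combined, SE = √[1/(22.5 + 18)] = 0.1571, about 0.5% larger (1% with persisting slopes).

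**The case against.** The strongest reply is that the plan may already cover this. An order test needs an order term in the fitted model, and an order-by-group test on the change scores is not weak: it has 83% power at a 0.5 SD difference and 99% at 0.75 SD. If the term is kept only when p < 0.05, then with 18 + 18 complete subjects power is 81–82% and type I error 4.9–5.0% at every difference from 0 to 1.0 SD, the same as always keeping it. That is correct, but it holds for balanced data under one favourable reading of order. At 22:14 and 0.5 SD, test-then-keep gives 77% power against 80%, and type I error of 5.7% against 5.1%. The plainest reading, a sequence main effect, gives no adjustment at all.

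Other points stand in part:

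- The large power losses need both a large period difference and an unstructured-type error. This is true, but the structure is to be chosen later, so the milder case cannot be assumed.
- Losing 6 of 18 from one order and none from the other is an assumption. With 2 or 3 lost, the bias is 16/34 − 0.5 = −0.029 or 15/33 − 0.5 = −0.045 per unit. Even with 6 lost, a 0.5 SD difference in change (0.5 × √0.8 = 0.447) gives a bias of 0.045, about 0.3 standard errors.
- Reading time as visit within period is an inference. The repeated visit labels make it the natural one.
- A sequence main effect changes neither the bias nor the standard error of the week-4 contrast. This is accepted; it is not the essential part of the fix.

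**Conclusion.** The concern holds. As written, the model has no period or period-by-time term, and only one unstated form of the order test would supply the adjustment that the group-by-time contrast needs. Two analysts could follow the text and fit different primary models.

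The consequence is bounded. With balanced, complete data there is no bias, the type I error does not rise above 5%, and the 80% power figure stands. The exposure is lost power (74% at an assumed 0.5 SD difference in change with an unstructured-type error, about 82% with variance components) and, under unequal loss, a bias of about 0.10 to 0.15 per unit difference in change. All period differences, variances and dropout patterns are assumptions, because the documents give none. The better method is close to free, so it is worth adopting as an improvement to the specification.

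**What to change.** In Statistical Considerations, General Strategy, add one sentence: the primary and secondary mixed models include group, time (visit within period), group-by-time, period and period-by-time as fixed effects, retained whatever any test shows. A sequence main effect can be added by convention; it does not alter the week-4 contrast.

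Then define the order test (sequence, order-by-group, or order-by-group-by-time), report it descriptively, and state that it will not be used to choose the model.

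With five visits per period the cost is six fixed-effect parameters: one for period, four for period-by-time and one for sequence. Power at d' = 0.49 goes from 81.6% to 81.5%, and the target of 36 subjects does not change.
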